8.5.4.6 Multiple comparison and multiplicity

Since the mean Hb values at Week 20 and Week 24 of the treatment period, the primary endpoints of this study, should be evaluated in the analysis of the fixed data of the treatment period phase 1, there is no need to consider multiplicity in the analysis of the final fixed data.

8.5.4.7 A study with active control intended to demonstrate equivalence. This is a non-inferiority study with an active control.

8.6 Safety analysis

The safety analysis set should be analyzed for each treatment group. When necessary, frequency and proportion should be calculated for discrete variables and descriptive statistics for continuous variables. Unless otherwise specified, no analysis will be performed for patient cohorts.

8.6.1 Adverse events and adverse drug reactions

8.6.1.1 Summary of adverse events and adverse drug reactions

The number (number of subjects with adverse events) and proportion of subjects in whom the following adverse events are observed at least once after the administration of the study drug to the end of the follow-up period should be calculated for each treatment group. The same analyses should be performed for the Correction and the Conversion cohorts.

- Adverse event
- Adverse drug reaction
- Serious adverse event
- Serious adverse drug reaction
- Adverse event leading to discontinuation
- Adverse events leading to dose reduction or interruption of study drug
- Adverse events treated with rescue therapy

- Adverse event leading to death (adverse event of fatal outcome)

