Attachment 1 Pregnancy Reports

Appendices

- Appendix 1 Administrative Structure
- Appendix 2 List of Study Centers and Investigators
- Appendix 3 Study Protocol Consent Form
- Appendix 4 EQ-5D-5L questionnaire
- Appendix 5 KDQOL questionnaire
- Appendix 6 Package Insert for Nesp® Injection

List of abbreviations

Abbreviation	Non-abbreviated term
AUC	Area under the plasma concentration-time curve
ANCOVA	Analysis of covariance
BCRP	Breast cancer resistance protein
CKD	Chronic kidney disease
C _{max}	Maximum plasma concentration
CYP	Cytochrome P450
DNA	Deoxyribonucleic acid
EDC	Electronic data capture/ Systems for using electronic devices and software to collect data on clinical study subjects from study centers or contract testing laboratories
eGFR	Estimated glomerular filtration rate
EPO	Erythropoietin
ESA	Erythropoiesis stimulating agent
FAS	Full analysis set
GFR	Glomerular filtration rate
GCP	Good Clinical Practice
HD-CKD	Hemodialysis dependent chronic kidney disease
HIF-PH	Hypoxia inducible factor prolyl hydroxylase
IC ₅₀	Median inhibitory concentration
JSĐT	The Japanese Society for Dialysis Therapy
LOCF	Last observation carried forward
MMRM	Mixed model repeated measures
MRP	Multidrug resistance-associated protein
NDD-CKD	Nondialysis dependent chronic kidney disease
OATP	Organic anion transporting polypeptide
OAT	Organic anion transporter
PD	Pharmacodynamics
P-gp	P-glycoprotein
PK	Pharmacokinetics
PT	Preferred term
PT-INR	Prothrombin time-international normalized ratio
PPS	Per protocol set
QOL	Quality of life
SOC	System organ class
t _{1/2}	Terminal elimination half-life
T _{max}	Time to reach maximum plasma concentration
TIBC	Total iron binding capacity
TSAT	Transferrin saturation

Definitions of Terms

Term	Definitions
Study period	From the day of informed consent to the final day of follow-up observation period
Treatment period	From the first day of the treatment period to the final day of the treatment period
Treatment period Phase 1	From completion of scheduled tests for the first day of the treatment period to completion of scheduled tests for Week 24 of the treatment period
Treatment period Phase 2	From completion of tests specified for Week 24 of treatment period to completion of tests specified for Week 52 of treatment period
Day of completion of treatment period	Week 52 of treatment period or day of discontinuation of treatment

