8.5.3 Rescue therapy

The following rescue therapy options will be available for subject safety. If any of the following rescue therapies are performed prior to scheduled tests at Week 24 of the treatment period, that subject will be withdrawn from the study. If rescue therapies are performed after scheduled tests at Week 24 of the treatment period, the subject can continue in the study unless investigators/subinvestigators determine study withdrawal is appropriate. Details of any rescue therapy implemented will be recorded in the subject's CRF.

(1) ESA formulations

If a subject has received maximum dosages of MT-6548 or darbepoetin alfa injection for ≥ 2 weeks and meets all criteria below, investigators/subinvestigators may administer ESA as rescue therapy to improve Hb levels if necessary in order to secure subject safety. ESA rescue therapy may also be administered without meeting the criteria below if deemed necessary by investigators/subinvestigators in order to secure subject safety, such as in cases of acute decreases in Hb. Study drug administration (MT-6548 or darbepoetin alfa injection) will be discontinued if implementing ESA rescue therapy. Study drug treatment may resume if Hb levels improve, as long as there is no concomitant use with ESA. Subjects who are not expected to resume study drug treatment will be withdrawn from the study.

Administration of any ESA formulation aside from darbepoetin alfa injection is considered rescue therapy for subjects in the darbepoetin group. Dosage increase of darbepoetin alfa injection (regardless of adherence to the dosage adjustment algorithm) does not constitute rescue therapy.

- ✓ Anaemia or anaemia symptoms (e.g., fatigue, weakness, shortness of breath, chest pain, confusion, dizziness) become aggravated compared to the first day of the treatment period to the point they are clinically problematic.
- ✓ Hb levels drop to < 8.0 g/dL.

(2) RBC transfusion

Normally RBC transfusions are performed when clinically necessary in instances of acute or major haemorrhaging. RBC transfusion may be performed at investigator/subinvestigator discretion if deemed clinically necessary in cases of potentially worsening anaemia, even if that

anaemia is not severe, or in cases of moderate to severe anaemia symptoms.

(3) Phlebotomy

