The investigator/subinvestigator will assess whether or not there is a logical possibility that the study drug caused the AE. This assessment will take into account factors not related to the study drug, including risk factors such as natural course and concurrent treatments for underlying or concomitant diseases, as well as the temporal relationship between the study drugs and the event (recurrence after resuming administration, elimination after discontinuation, etc.). AEs for which a logical possibility exists for causal relationship with the study drug are treated as ADRs.

1. Logical possibility
2. No logical possibility

5) Outcome

AE outcomes are classified as follows:

1. Recovery
2. Relief
3. Not recovered
4. Recovered with sequelae
5. Death
6. Unknown

6) Date of outcome

Date of outcome is determined according to the following criteria:

Recovery: Date of recovery. If date of recovery is not known, use date on which recovery was confirmed or determined.

Relief: Date on which relief was confirmed or determined.

Not recovered: Date on which “not recovered” was confirmed or determined.

Recovered with sequelae: Date on which “recovered with sequelae” was confirmed or determined.

Death: Date of death. If date is not known, use date of confirmation or determination.

Unknown: Date of death if outcome is unknown due to death of subject for cause other than the relevant AE. For other circumstances use date of confirmation or determination.

7) Action taken with the study drug

Actions taken with the study drug are classified into the following six categories:

1. Discontinuation of administration (study withdrawal)
2. Drug holiday
3. Dosage increase
4. Dosage reduction
5. No action
6. Not applicable (occurred after final administration of study drug)

[figure not shown]
8) Action taken other than with the study drug

Actions taken other than with the study drug are classified into the following two categories:

If actions other than with the study drug were taken, details of these will be investigated and recorded in the CRF.

1. No
2. Yes

9) Follow-up investigation

- Period [1] above is the 14 days from the day after completion of the treatment period, during which any AEs will be investigated.
- Period [2] above is the 28 days from the day after completion of the follow-up observation period; it is the period for follow-up investigations of AEs occurring during the safety evaluation period (treatment period + Period [1]).

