12.1 Withdrawal criteria

Subjects will be withdrawn from the study if the following criteria are met:

- (1) If the subject expresses a desire to withdraw from the study.
- (2) If it is discovered that the subject is clearly ineligible for study participation.
- (3) If investigators/subinvestigators determine that AEs make continued participation in the study difficult.
- (4) If the subject meets one of the following criteria regarding hepatic function abnormalities during the study.
 - 1) ALT or AST > 3x ULN and total bilirubin > 2x ULN
 - 2) ALT or AST > 3x ULN and INR > 1.5^{*1}
 - 3) ALT or AST > 8x ULN
 - 4) ALT or AST remains > 5x ULN over 2 weeks^{*2}
 - 5) ALT or AST > 3x ULN with symptoms including e.g., fatigue, nausea, vomiting, right upper quadrant pain, fever, rash or eosinophilia

*1: The subject should be withdrawn from the study if the measurement of PT-INR is performed besides this study and the value meets the criterion.

*2: Administration of the study drug should be avoided with ALT or AST > 5x ULN unless there are no other good therapeutic options.

- (5) If rescue therapy is performed prior to conclusion of scheduled tests at Week 24.
- (6) If investigators/subinvestigators determine that continuation of the study is inappropriate for a subject, such as if hyperviscosity syndrome occurs or if control of Hb within the target range is impossible.
- (7) If continuous haemodialysis or peritoneal dialysis is initiated, or if the subject receives a renal transplant.
- (8) If pregnancy of the subject is discovered.
- (9) If the investigator/subinvestigator determines a subject should withdraw from the study for any other reason.

Rationale

- (1) Set out of ethical considerations.
- (2) (7) Set in order to prevent study drug administration to subjects unsuitable for inclusion in safety

or efficacy evaluation.

- (3) (4) (6) (8) Set out of safety considerations.
- (5) Set because evaluating efficacy of MT-6548 accurately would be difficult.
- (9) Set in order to allow the investigator/subinvestigator to make determinations regarding study continuation for significant safety-related reasons other than those enumerated above.

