8.6.1.5 Adverse events by dose immediately before onset

The number and incidence rate of adverse events and adverse drug reactions in overall and individual events classified by SOC and PT per total exposure period should be calculated for each treatment group by dose immediately before onset*. The total exposure period is defined as the total number of months (months) that each dose was administered during the study period.

The following formula is used to calculate the number of months of exposure. Number of months of exposure = number of days of exposure/30.4375

*The tabulation unit for each event by dose immediately before onset should be as follows:

MT-6548 group: daily dose (tabulation unit: 0 mg, 150 mg, 300 mg, 450 mg, 600 mg)

Darbepoetin group: weekly dosage (tabulation unit: 0 µg, >0 µg to ≤30 µg, >30 µg to ≤60 µg, >60 µg to ≤90 µg, >90 µg to ≤120 µg, >120 µg)

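### Headline adverse-event tables are crude subject proportions with no overall rate per patient-year by arm, although observation time ends 14 days after discontinuation and can differ between arms

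*SAP*

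**What the plan says.** **AE summary.** Final SAP 8.6.1.1 requests "The number (number of subjects with adverse events) and proportion of subjects in whom the following adverse events are observed at least once", from first dose to the end of follow-up. Section 8.6.1.2 does the same by system organ class (SOC) and preferred term (PT). Phase 1 SAP 8.6.1.1 and 8.6.1.2 match, except that counting stops at Week 24 for continuing subjects and at the end of follow-up for those who discontinued.

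**Length of the AE window.** Protocol 9.2.4.2 states: "Period [1] above is the 14 days from the day after completion of the treatment period, during which any AEs will be investigated". The later 28-day period only follows up AEs already seen. The Protocol's Definitions of Terms puts completion of the treatment period at "Week 52 of treatment period or day of discontinuation of treatment", so a subject who leaves early contributes new AEs for two more weeks only.

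**Rescue and withdrawal.** Under Protocol 8.5.3, if any rescue is given "prior to scheduled tests at Week 24 of the treatment period, that subject will be withdrawn from the study". Protocol 12.1, criterion (5), repeats this. For ESA rescue the definition differs by arm. Any ESA given to an MT-6548 subject is rescue. In the darbepoetin arm only a different ESA counts, and "Dosage increase of darbepoetin alfa injection (regardless of adherence to the dosage adjustment algorithm) does not constitute rescue therapy".

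**Tables that use time.** Section 8.6.1.4 of each SAP tabulates AEs by 12-week onset interval, with the subjects at each time point as denominator. Section 8.6.1.5 gives rates over exposure, but by dose just before onset; in the final SAP, "The total exposure period is defined as the total number of months (months) that each dose was administered during the study period".

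**The concern.** A crude proportion compares arms fairly only if both are watched for about the same time. Here the window closes two weeks after a subject leaves, and one reason for leaving is defined differently by arm. If more ESA is judged necessary before Week 24, an MT-6548 subject who receives it is withdrawn, while a darbepoetin subject can receive more darbepoetin, stay in and go on contributing AEs.

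The tables that use time do not close the gap. Section 8.6.1.4 compares arms slice by slice and gives no whole-period figure. The bands in 8.6.1.5 are mg per day in one arm and µg per week in the other, so no band in one arm matches a band in the other.

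At stake is the by-arm reading of AEs, serious AEs (SAEs), adverse drug reactions (ADRs) and deaths in a trial that lists long-term safety of MT-6548 among its objectives. Unequal observation time produces a systematic difference that the interval around a crude proportion does not reflect.

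**Working it through.** The documents state no figure for AE observation time, withdrawal or rescue by arm, so there is no plan figure to reproduce on this point. Excess withdrawal, its timing and the event rate below are assumptions.

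**Inputs from the documents:** 52 weeks of treatment plus 2 weeks of follow-up, a 54-week window (final SAP); counting to Week 24 for continuing subjects (Phase 1 SAP); 150 subjects per arm.

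**Assumed:** a share e of MT-6548 subjects withdrawn in excess of darbepoetin, at Week 12; a constant first-event rate r, equal in both arms (central value 0.4 per year, range 0.2 to 1.0).

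**1. Window lost by one subject withdrawn at week t:** 1 − (t + 2)/54.
- Week 4: 1 − 6/54 = 89%
- Week 12: 1 − 14/54 = 74%
- Week 20: 1 − 22/54 = 59%

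**2. Mean MT-6548 window and crude proportion (final SAP).** The mean window is 54 − 40e weeks. At r = 0.4:
- full window: 1 − exp(−0.4 × 54/52) = 1 − 0.660 = 34.0%
- 14-week window: 1 − exp(−0.4 × 14/52) = 1 − 0.898 = 10.2%
- MT-6548 arm: (1 − e) × 34.0% + e × 10.2%

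| e | Mean window (weeks) | Person-time lost | Crude, MT-6548 | Crude, darbepoetin | Difference (points) |
|---|---|---|---|---|---|
| 5% | 52.0 | 3.7% | 32.8% | 34.0% | −1.2 |
| 10% | 50.0 | 7.4% | 31.6% | 34.0% | −2.4 |
| 15% | 48.0 | 11.1% | 30.4% | 34.0% | −3.6 |
| 20% | 46.0 | 14.8% | 29.2% | 34.0% | −4.8 |

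Sampling standard error of the difference: √(2 × 0.34 × 0.66/150) = 5.5 points.

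**3. Masked hazard ratio.** This is the true MT-6548 to darbepoetin hazard ratio at which the two crude proportions come out equal. At r = 0.4 and e = 15% it is 1.15. Over r = 0.2 to 1.0 it is 1.04 to 1.06 at e = 5%, and 1.09 to 1.28 for e = 10% to 20%.

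**4. Same case on a person-time basis.** Mean time to first event or end of window is (crude proportion)/r. For e = 15%:
- darbepoetin: 0.340/0.4 = 0.850 years
- MT-6548: 0.304/0.4 = 0.761 years
- first events per 100 patient-years: 34.0/0.850 = 40.0 and 30.4/0.761 = 40.0

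Under a constant hazard unrelated to withdrawal, the artefact disappears.

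**5. Phase 1 SAP.** Withdrawal at Week 12 leaves 14 of 24 weeks, a loss of 1 − 14/24 = 42%; at Week 20 the loss is 1 − 22/24 = 8%. At r = 0.4 and e = 15%, 1 − exp(−0.4 × 24/52) = 16.9% compares with 0.85 × 16.9% + 0.15 × 10.2% = 15.9%. The difference is 1.0 point and the masked hazard ratio about 1.07. The 54-week figures do not carry over to this SAP.

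**The case against.** **Narrow mechanism.** The asymmetry covers ESA rescue only, and withdrawal is automatic only before Week 24. Transfusion, phlebotomy and a non-darbepoetin ESA remove darbepoetin subjects as well. MT-6548 can itself be raised from 300 to 600 mg, and the listed ESA-rescue criteria call for at least 2 weeks at maximum dose, worsened symptoms and Hb below 8.0 g/dL, though investigators may act outside them. Likely early rescue is an exclusion criterion. All of this stands and limits the excess one should expect.

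**Unknown direction.** A reader might infer that the MT-6548 arm will have the shorter window and so look safer. The documents do not support that. They give no rates by arm, and withdrawals for AEs, liver tests, dialysis, uncontrolled Hb or consent could go either way.

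**Objective.** A reader might also take safety relative to darbepoetin to be a stated objective. The text names only the safety of long-term MT-6548; darbepoetin is the control for Hb, and AE reporting is descriptive.

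**Existing outputs.** The final SAP reports discontinuations by arm and 12-week interval (8.2.2), treatment duration by arm (8.4) and rescue by arm (8.5.2 (4)). These would reveal unequal follow-up, and 8.6.1.4 partly allows for it. None yields a whole-period AE comparison, unless exposure is shown for each band in 8.6.1.5 and the reader sums it.

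**Limits of the remedy.** If the subjects who leave have a different event risk, person-time rates do not remove that bias. This is correct and must be stated with the rates.

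**Conclusion.** The gap is real and cheap to close. The headline AE tables ignore observation time, that time can differ by arm through a rule in the Protocol, and no whole-period rate per arm is planned. Taken alone, the ESA-rescue rule pushes toward a shorter MT-6548 window; the net direction and size cannot be known from the documents.

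The size is modest unless excess withdrawal is large. At 5% excess the artefact is well below sampling error; a masked hazard ratio of 1.15 in the final analysis needs 15% excess at Week 12, which nothing in the documents establishes. These figures rest on the assumed excess, its timing, a constant hazard and withdrawal unrelated to risk. The case for acting does not depend on which arm is shorter, because a rate per patient-year corrects unequal duration either way. It supplements the crude tables and does not replace them.

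**What to change.** In 8.6.1.1 and 8.6.1.2 of both SAPs, keep the crude counts and proportions and add beside them, by arm:

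- total AE observation time;
- subjects with a first event per 100 patient-years, with time from first dose to the earlier of the first event or the end of the safety evaluation period (in the Phase 1 SAP, cut at Week 24 for continuing subjects);
- the between-arm rate difference or ratio with 95% CI for any AE, SAE, ADR and fatal AE;
- rates by PT.

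State that the rates assume a roughly constant hazard, which the onset-interval table in 8.6.1.4 can check, and non-informative withdrawal, which should be reported as a limitation.

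The cost is a few tables and some SAP wording. Dosing, AE onset and discontinuation dates are already collected, and final SAP 8.6.1.5 already defines the conversion to months. Data collection and the rescue and withdrawal rules are untouched.

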8.6.1.2 Individual adverse events

For adverse events, adverse drug reactions, serious adverse events, serious adverse events, non-serious adverse events, adverse events leading to discontinuation, adverse events leading to dose reduction or interruption of study drug, adverse events treated with rescue therapy, and adverse events leading to death, the number and proportion of subjects with each adverse event classified by SOC and PT in MedDRA/J version: 20.1 (hereinafter the same) should be calculated. The same analyses should be performed for the Correction and Conversion cohorts except non-serious adverse events.

The SOC will be sorted by order of international consensus, the PT by descending order of the number of subjects with MT-6548 and by descending order of the number of subjects with darbepoetin (PT code ascending when the number is equal).

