13.3.3 Safety

(1) Analysis methods for AEs and ADRs

The following statistics will be shown by treatment group: numbers of subjects and incidence ratios for AEs, SAEs, AEs leading to discontinuation, AEs leading to death, ADRs, serious ADRs, ADRs leading to discontinuation, and ADRs leading to death.

(2) Analysis methods for laboratory values, resting standard 12-lead ECG, body weight, vital signs, fundoscopy, and chest X-ray

Descriptive statistics will be calculated for continuous data at each timepoint by treatment group. Descriptive statistics will also be calculated for changes from baseline by treatment group. A shift table will be shown for changes of discrete data from baseline to each timepoint by treatment group.

(3) Analysis methods for ratios of subjects with Hb levels of ≥ 13.0 g/dL or ≥ 14.0 g/dL.

Numbers and ratios of subjects with Hb levels of ≥ 13.0 g/dL or ≥ 14.0 g/dL at each timepoint will be shown by treatment group.

(4) Ratio of subjects with Hb increase rates exceeding 0.5 g/dL/week.

Numbers and ratios of subjects with rate of Hb increase of > 0.5 g/dL/week will be shown by treatment group.

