8.7.4 Individual adverse events

(1) Summary of adverse events and adverse drug reactions

The number (number of subjects with adverse events) and proportion of subjects in whom the following adverse events are observed at least once after the administration of the study drug to the end of the follow-up period should be calculated for each treatment group. Unless otherwise specified, no analysis will be performed for patient cohorts.

- Adverse event
- Adverse drug reaction
- Serious adverse event
- Serious adverse drug reaction
- Adverse event leading to discontinuation
- Adverse events leading to dose reduction or interruption of the study drug (active drug)
- Adverse events resulting in death (adverse event leading to death)

(2) Individual adverse events

If a difference from treatment period 1 occurs in “(1) Summary of adverse events and adverse reactions”, the number of subjects and the incidence rate of individual adverse events classified by SOC and PT in MedDRA Version 20.1 and MedDRA/J Version 20.1. (hereinafter the same) should be calculated.

The SOC will be sorted by order of international consensus, the PT by descending order of the number of subjects with MT-6548 and by descending order of the number of subjects with darbepoetin (PT code ascending when the number is equal). Unless otherwise specified, no analysis will be performed for patient cohorts.

(3) Fundoscopy

The frequency of each decision result (normal, clinically nonsignificant abnormal, or clinically significant abnormal [Presence or absence of retinal hemorrhage, presence or absence of retinal oedema]) should be calculated at each evaluation time point, and a shift table composed of the decision results (normal, clinically nonsignificant abnormal, or clinically significant abnormal) should be provided on the first day of the treatment period and each evaluation time point.

9. Software to Use

SAS for Windows (Release 9.4) will be used for statistical analysis.

10. Changes in the Statistical Analysis Plan from the Study Protocol

No change from the study protocol.

11. References

Errata

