16.1.9 Documentation on Statistical Methodology

Confidential

The Statistical Analysis Plan (Version 2) in “A Phase III, Open-label, Confirmatory Study of MT-6548 Compared to Darbepoetin Alfa in Non-dialysis Subjects with Anemia Associated with Chronic Kidney Disease in Japan” is corrected as follows:

Applicable part	Correct
4.12 Iron supplement dosage	(Error) *5: In this tabulation, 1 month month is counted as 30.4375 days (365.25/12 = 30.4375). (Correct) *5: In this tabulation, 1 month month is counted as 30.4375 days (365.25/12 = 30.4375). (Reason) Due to typographical error.

Applicable part	Correct
8.2.2 Subjects who discontinued or interrupted their treatment	(Error) Item: Number and proportion of drug interruptions among subjects enrolled in the treatment period (Correct) Item: Number of and proportion drug interruptions among subjects enrolled in the treatment period (Reason) Deleted because it was an unnecessary description

Applicable part	Correct
Table 8.5.4.6 Subgroup analysis on efficacy	(Error) CYP2B6 inducer coadministration * List of CYP2B6 inducers obtained from The Metabolism and Transport Drug Interaction Database (DIDB®). (Correct) CYP2B6 substrates * List of CYP2B6 substrates obtained from The Metabolism and Transport Drug Interaction Database (DIDB®). (Reason) Due to typographical error

Applicable part	Correct
8.6.1.2. Individual adverse events	
(Error) For adverse events, adverse drug reactions, serious adverse events, non-serious adverse events, serious adverse events, adverse events leading to discontinuation, dose reduction or interruption of study drug, and adverse events leading to death, the number of subjects with individual adverse events classified by SOC and PT in MedDRA/J version: 2x.x (hereinafter the same) and the incidence should be calculated.
 
(Correct) For adverse events, adverse drug reactions, serious adverse events, non-serious adverse events, serious adverse drug reactions, adverse events leading to discontinuation, adverse events leading to dose reduction or interruption of study drug, and adverse events leading to death, the number of subjects and incidence rate will be calculated for each adverse event classified by SOC and PT in MedDRA/J 20.1 (hereinafter the same).
 
(Reason) Due to typographical error.

Applicable part	Correct

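### Neither SAP specifies the counts of adverse drug reactions leading to discontinuation and to death that protocol 13.3.3(1) requires, and neither declares the change

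*SAP*

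**What the plan says.** Protocol 13.3.3(1) sets out what will be shown by treatment group for adverse events (AEs) and ADRs. Four categories concern AEs of any cause: all, serious, leading to discontinuation, and leading to death. The other four mirror these for events judged drug-related: "ADRs, serious ADRs, ADRs leading to discontinuation, and ADRs leading to death".

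The summary list in final SAP 8.6.1.1 keeps "Serious adverse drug reaction", but for withdrawals it has only "Adverse event leading to discontinuation" and for deaths only the any-cause row. Phase 1 SAP 8.6.1.1 does the same. So does final SAP 8.7.4, which re-tabulates Phase 1 data.

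Section 8.6.1.2 of both SAPs lists the categories to be broken down by system organ class and preferred term (SOC/PT). In both, the printed list includes "serious adverse events, serious adverse events, non-serious adverse events, adverse events leading to discontinuation". Serious AEs appear twice and serious ADRs do not appear. An erratum gives a corrected list for a section 8.6.1.2: "serious adverse events, non-serious adverse events, serious adverse drug reactions, adverse events leading to discontinuation".

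On departures from the protocol, final SAP section 10 and Phase 1 SAP section 9 say the same thing: "No change from the study protocol". Protocol 13.4 requires the reasons for any change to the analysis plan to be given in the SAP and in the clinical study report.

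**The concern.** Long-term safety of MT-6548 is a stated objective of the study, and these are the protocol's own safety outputs. If the SAP lists are followed as written, the summary shows by arm how many subjects had an AE of any cause that led to withdrawal or death. It gives no separate row for how many of those events were judged drug-related. A reader of the SAPs would also believe that nothing had been dropped, because each one states that the protocol is unchanged.

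**Working it through.** No calculation in the plan is at issue, so the check is a comparison of lists. Rows are the eight categories in protocol 13.3.3(1); columns are the SAP lists as printed.

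| Protocol category | Phase 1 SAP 8.6.1.1 | Final SAP 8.6.1.1 | Final SAP 8.7.4(1) | Phase 1 SAP 8.6.1.2 | Final SAP 8.6.1.2 |
|---|---|---|---|---|---|
| AEs | yes | yes | yes | yes | yes |
| Serious AEs | yes | yes | yes | yes (twice) | yes (twice) |
| AEs leading to discontinuation | yes | yes | yes | yes | yes |
| AEs leading to death | yes | yes | yes | yes | yes |
| ADRs | yes | yes | yes | yes | yes |
| Serious ADRs | yes | yes | yes | no | no |
| ADRs leading to discontinuation | no | no | no | no | no |
| ADRs leading to death | no | no | no | no | no |
| Covered | 6 of 8 | 6 of 8 | 6 of 8 | 5 of 8 | 5 of 8 |

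The protocol list does not ask for an SOC/PT breakdown. The contradiction with the protocol therefore lies in the summary lists; the 8.6.1.2 columns show that the two counts do not turn up there either. The additional SAP of 6 September 2019 adds one table of AEs by SOC and PT and does not fill the gap.

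**Can the missing counts be derived from the rows that remain?** Let a be the number of subjects with any ADR and d the number with any AE leading to discontinuation. A subject may be counted in both because of two different events. The number with an ADR that led to discontinuation can therefore lie anywhere from 0 to min(a, d). The serious ADR row does not settle it, because an ADR that leads to withdrawal need not be serious. For deaths the position is better: protocol 9.2.4.2 classes every fatal event as serious, so each fatal ADR is inside the serious ADR count. That row does not separate fatal from non-fatal events, so the number of fatal ADRs is bounded but not shown.

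**Which SAP does the erratum correct?** It names Version 2, which fits both SAPs, so the numbering has to decide.

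- It places iron supplement dosage at 4.12. That is the Phase 1 number; the final SAP has it at 4.11.
- It cites Table 8.5.4.6 for efficacy subgroups. That is the Phase 1 number; the final SAP uses Table 8.5.4.5.1.
- Its error text has the MedDRA placeholder 2x.x, which is printed in Phase 1 SAP 8.6.1.2. The final SAP already has 20.1.
- Its corrected list has no item for AEs treated with rescue therapy, which final SAP 8.6.1.2 contains.

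The erratum thus fits the Phase 1 SAP, where it raises 8.6.1.2 from 5 to 6 of 8. The wording in the final SAP is left as printed.

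**The case against.** A reader might infer that drug-related withdrawals and deaths will not be tabulated at all. The documents do not support that. Both SAPs' contents pages name lists of output tables and listings that are not in the text available for this review, so a table or listing of these events cannot be ruled out. What can be said is that the analysis sections specify no separate count.

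A reader might also tie the repeated item in 8.6.1.2 to the missing withdrawal and death counts. It has no bearing on them. It touches only the SOC/PT table of serious ADRs, and serious ADRs are counted in 8.6.1.1 of both SAPs. The SAP is a translation from Japanese, and the erratum's reason for the entry is a typographical error, so the repetition may be no more than a translation slip. The intended term is clear from the erratum and from the order of the summary list. This stands, and is why the repetition is treated here as an editorial note.

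The strongest remaining argument is that little information is lost. Withdrawals are tabulated by reason and arm (final SAP 8.2.2), and ADRs by SOC/PT, severity, onset, dose and cumulative dose. In an open-label trial where the investigator assigns causality, the any-cause rows depend less on judgement. The SOC/PT tables could also narrow the range: a preferred term that appears among AEs leading to discontinuation but not among ADRs cannot be drug-related. All of this limits the consequence. It does not supply the two counts, and it does not make the statement of no change correct.

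**Conclusion.** The point holds as a contradiction between the protocol and both SAPs. Two of the eight safety categories that the protocol specifies have no separate count in any of the five SAP lists, and neither SAP declares this. The loss is real for ADRs leading to discontinuation, which the other rows do not determine. It is smaller for fatal ADRs, which are contained in the serious ADR count but not shown apart.

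The impact is limited to descriptive safety reporting. No efficacy result, test or confidence interval for efficacy is affected. The conclusion rests on the analysis sections as printed; it would reduce to a wording mismatch if the output-table lists turned out to include the two categories.

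The repeated item in final SAP 8.6.1.2 is a separate editorial matter that concerns only the SOC/PT table.

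**What to change.** Add ADRs leading to discontinuation and ADRs leading to death to 8.6.1.1 and 8.6.1.2 of both SAPs, and to final SAP 8.7.4. This takes each summary list from 6 to 8 of 8. If the sponsor prefers to leave them out, it should replace the statement of no change with a declared and justified departure, as protocol 13.4 requires.

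As an editorial correction, replace the second mention of serious AEs in final SAP 8.6.1.2 with serious ADRs, the term the erratum uses. With both changes that list goes from 5 to 5 + 1 + 2 = 8 of 8.

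The cost is SAP wording and a few table rows. Protocol 9.2.4.2 already has causality, action taken with the study drug and outcome classified for each event, so no new data are needed.
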